RQ2: Compared to the table, will the risk ladder elicit higher risk perceptions, response efficacy, worry, affective reactions to information, affective attitudes to exercise, and anticipated regret?

Sociodemographic exploratory research questions

RQ3: Will education, race/ethnicity, numeracy, health literacy, and/or graph literacy moderate the effect of risk communication strategy on primary outcomes?

MENTAL IMAGERY

To test whether supplementing the risk calculator with a mental imagery-based self-regulation intervention will increase actual engagement in physical activity over time, and to explore several possible mechanisms.

Primary outcome and exploratory research questions

H5: Engagement in physical activity will increase from baseline to 90-day follow-up only among individuals in the physical activity mental imagery intervention,^[5, 7-9] not in the sleep hygiene imagery active control condition.

RQ5: Will education, race/ethnicity, numeracy, health literacy, and/or graph literacy moderate the effect of mental imagery condition on behavior?

Secondary outcomes and exploratory research questions

H6: Within the physical activity mental imagery condition, increases in activity from pre-intervention baseline to 90-day follow-up will be preceded by the following measures assessed at the week 4 follow-up: action planning, coping planning, action self-efficacy, maintenance self-efficacy, recovery self-efficacy, affective attitudes to exercise, and perceived vividness of imagery.^[5, 7-9, 16]

RQ6: Within the physical activity mental imagery condition, the direction and magnitude of change in activity from pre-intervention baseline to week 1 follow-up will be preceded by the following measures assessed at the survey assessed immediately post-intervention: action planning, coping planning, action self-efficacy, maintenance self-efficacy, recovery self-efficacy, affective attitudes to exercise, and perceived vividness of imagery.^[5, 7-9, 16] Similarly, measures assessed at week 1 will predict change in behavior from week 1 to week 2; measures assessed at week 2 will predict behavior change from week 2 to week 3; and measures assessed at week 3 will predict behavior change from week 3 to week 4.

Eligibility Criteria

RISK CALCULATOR AND MENTAL IMAGERY

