All hypotheses and research questions will be examined using separate analyses for each outcome variable. Assumptions of each type of test will be checked (e.g., assumptions of normality and homogeneity of variance for ANOVAs). If there are violations, non-parametric tests will be used instead. Sex will be a covariate because there are no valid prediction models for male breast cancer, so men will not be shown a breast cancer risk estimate. The inclusion of other personal characteristics as covariates will be determined by the results of the preliminary analyses. Tests of moderation will be conducted by creating interaction terms between the risk presentation condition or mental imagery condition variables, as appropriate, and the variable assessing the moderator of interest. All statistical tests will be based on list-wise deletion except structural equation models, which can accommodate missing data.

Mediation analyses will be conducted using structural equation modeling (SEM). Full Information Maximum Likelihood estimation (FIML)^[44] will be used to allow the inclusion of missing data. Standardized estimates will be calculated and bias-corrected bootstrapping will be used to obtain the 95% confidence intervals.^[45-48] Criteria assessing model fit will also be examined (e.g., Standardized Root Mean Square Residual $\leq .08$, comparative fit index $\geq .95$, root mean square error of approximation $\leq .06$).^[49, 50] Mediation analyses will examine each construct as an individual mediator first, and then as a multiple mediator model.

Table 2 below describes the analyses that will be conducted for each hypothesis or research question.

Table 2. Overview of Statistical Analyses

	Priority	Statistical test(s)	Outcomes	Predictors/Mediators/Moderators
Risk Calculator				
H1; RQ1	Primary	3 arm ANOVA, 2 planned contrasts (risk ladder vs. text; risk ladder vs. table)	Comprehension, intentions	Predictor: Risk presentation condition
H2	Secondary	SEM	Intentions	Predictor: Risk presentation condition (risk ladder vs. text) Mediators: comprehension, risk perceptions, response efficacy, worry, affective reactions to information, affective attitudes to exercise, anticipated regret
H3	Secondary	3 arm ANOVA, planned contrast (risk ladder vs. text)	Change in physical activity (mins/week at 90 days – mins/week at baseline)	Predictor: Risk presentation condition

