H4	Secondary	SEM	Change in physical activity (mins/week at 90 days – mins/week at baseline)	Predictor: Risk presentation condition (risk ladder vs. text) Mediator: Intentions
RQ2	Secondary	3 arm ANOVA, planned contrast (risk ladder vs.	Risk perceptions, response efficacy, worry, affective reactions to information, affective attitudes	Predictor: Risk presentation condition

table) to exercise, anticipated regret

RQ3 Secondary 3 arm ANOVA Comprehension, intentions Predictor: Risk presentation condition
Moderators: Education, race/ethnicity, numeracy, health and graph literacy

Mental Imagery

H5	Primary	T-test	Change in physical activity (mins/week at 90 days – mins/week at baseline)	Predictor: Mental imagery condition
RQ5	Primary	ANOVA	Change in physical activity (mins/week at 90 days – mins/week at baseline)	Predictor: Mental imagery condition Moderators: Education, race/ethnicity, numeracy, health and graph literacy
H6	Secondary	Regression (physical activity mental imagery condition only)	Change in physical activity (mins/week at 90 days – mins/week at baseline)	Predictors: Week 4 action planning, coping planning, action self-efficacy, maintenance self-efficacy, recovery self-efficacy, affective attitudes to exercise, perceived vividness
RQ6	Secondary	Regression (physical activity mental imagery condition only)	Weekly change in minutes of physical activity, assessed by 4 difference scores: Week1-Baseline; Week2-Week1; Week3-Week2; and Week4-Week3	Predictors: For each weekly behavioral assessment, use the previous week's measures of the following constructs: action planning, coping planning, action self-efficacy, maintenance self-efficacy, recovery self-efficacy, affective attitudes to exercise, perceived vividness.

Sample Size Calculations

We will enroll 500 participants at baseline. This will enable us to test the primary hypothesis for each of the components of the study. This calculation was based on the information below.

RISK CALCULATOR

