Sample size was calculated to be able to detect an effect of risk presentation strategy on the primary outcome variables comprehension and intentions (Risk Calculator Hypothesis 1 and RQ1). Based on a 2-sided test of means for 3 groups (ANOVA) at 80% power, $\alpha=.05$, $df=2$, and Cohen's f effect size of 0.15 (approximately equivalent to Cohen's d of 0.3),^[51, 52] we anticipate needing 432 participants. The effect size estimate was based on a study of personalized breast cancer risk and risk reduction communication that found an effect on intentions to increase physical activity of approximately $f=0.25$ and an effect on response efficacy of approximately $f=0.20$.^[4] However, most of those participants were white, highly educated, had high health literacy, and recruited from a breast health center. Thus, we can expect the findings in our more diverse sample to be somewhat lower. We chose $f=.15$ as a reasonable compromise because it represents slightly more than a minimal effect,^[53] but is also logistically feasible. To account for the possibility of 10% missing data in Baseline Survey 1, which assesses the constructs for the Risk Calculator Hypothesis 1, we would need to enroll 480 participants to obtain 432 completed surveys.

MENTAL IMAGERY

[name] prior self-regulatory intervention accounted for approximately 20% of the unique variance in physical activity at 4-week follow-up.^[5] This is approximately equivalent to a Cohen's d effect size of 1.0, which is considered a large effect.^[53] Because our follow-up is 90 days, we can expect that our effect size will be somewhat lower. Other self-regulation interventions yielded smaller effects over varying timeframes (e.g., $d=0.28-0.78$).^[7] Thus, powering the study to detect an effect of $d=0.30$ of the intervention on behavior (Mental

Imagery Hypothesis 5) would be conservative and reasonable. Based on a 2-sided test of means for 2 groups (t-test) at 80% power, $\alpha=.05$, and Cohen's d effect size of 0.30,^[51, 52] we anticipate needing 352 participants at 90-day follow-up. To account for the possibility of 30% attrition rate due to our underserved sample (unpublished data), we expect needing to enroll 500 participants at baseline to achieve this goal.

Study Procedure Calendar

	Year 1				Year 2				Year 3				Year 4			
	1	2	3	4	1	2	3	4	1	2	3	4	1	2	3	4
Startup (hiring, IRB amendments)	X	X	X	X					X							
Biweekly research team meetings	X	X	X	X	X	X	X	X	X	X	X	X	X	X	X	X

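### Table 2 ranks the five RQ5 moderator tests as Primary beside H5 with no error control, raising the imagery component's chance of a false primary result from 5% to about 26%

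*Combined protocol and SAP*

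**What the plan says.** Table 2 (Statistical Considerations, Main Analyses) marks three rows Primary.

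- **H1; RQ1:** a three-arm ANOVA with two planned contrasts (ladder against text, ladder against table) on each of two outcomes, comprehension and intentions.
- **H5:** one t-test of imagery condition on change in physical activity.
- **RQ5:** the effect of imagery condition on the same outcome, moderated by "Education, race/ethnicity, numeracy, health and graph literacy", which makes five moderators.

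The RQ3 row lists the same moderators for risk presentation condition and is labelled Secondary. The Objectives place H5 and RQ5 together under "Primary outcome and exploratory research questions"; H5 is the only hypothesis there.

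Main Analyses states: "All hypotheses and research questions will be examined using separate analyses for each outcome variable". Moderation is to be tested by adding an interaction term for the moderator in question. The plan states no multiplicity adjustment, alpha split, testing order or gatekeeping.

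Alpha appears only under Sample Size Calculations. The opening paragraph there says of the 500 participants: "This will enable us to test the primary hypothesis for each of the components of the study". The risk calculator figure covers H1 and RQ1, and the imagery figure covers H5. RQ5 has no sample-size basis.

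**The concern.** The Priority column decides what may later be presented as a primary result. As it stands, any one of five interaction tests could be reported as a primary finding of the imagery component even if H5 is null. Race and education are the variables on which recruitment is stratified, so a nominally significant moderator there would draw attention.

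These tests are also weakly powered. The same question asked of the other factor (RQ3) ranks lower, and the plan gives no reason for the difference.

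The risk calculator component has a milder version of the problem. Four contrasts share Primary status, two of them belong to RQ1, which is also listed among exploratory questions, and the plan does not say what pattern of results would count as support for H1.

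**Working it through.** **1. The plan's own figures.** All reproduce at an unadjusted two-sided 0.05.

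- Risk calculator: "Based on a 2-sided test of means for 3 groups (ANOVA) at 80% power", with f = 0.15. The noncentral F calculation gives N = 431.2, so 432 (power 80.1%). Allowing for 10% missing: 432 / 0.90 = 480, as stated.
- Imagery: "Based on a 2-sided test of means for 2 groups (t-test) at 80% power, $\alpha=.05$, and Cohen's d effect size of 0.30". The noncentral t calculation gives 175.4 per arm, so 176 × 2 = 352, as stated. Allowing for 30% attrition: 352 / 0.70 = 503 against the stated 500, which is close enough.

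The imagery sample size therefore supports one test, H5, at 0.05.

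**2. Imagery component, as labelled.** There are six Primary tests: H5 and five interactions. Assume each is run at 0.05, each moderator gets one test and all nulls are true.

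- Independent tests: 1 − 0.95^6 = 1 − 0.735 = 26.5%.
- The documents give no correlation among the five interaction statistics, so it was varied from 0 to 0.5 in a simulation of 500,000 null trials. The chance that at least one of the five is significant runs from about 22.5% (correlation 0) to 18.2% (correlation 0.5). Adding H5 as independent: 1 − 0.95 × (1 − 0.225) = 26.4%, and 1 − 0.95 × (1 − 0.182) = 22.3%.
- H5 alone primary: 5%.

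**3. Power of an RQ5 test (illustration).** Assume a binary moderator split 50/50, 352 completers (88 per cell) and unit SD. The standard error of the interaction is √(4/88) = 0.213. For an interaction as large as the whole H5 effect, 0.30 / 0.213 = 1.41, and power is about Φ(1.41 − 1.96) = 29%, against 80% for H5.

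**4. Risk calculator component.** There are 2 contrasts × 2 outcomes = 4 tests. The two contrasts share the ladder arm, so they correlate at 0.5. The correlation between outcomes is not given and was varied from 0 to 0.7.

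| Reading of the plan, all nulls true | Chance of at least one false positive |
|---|---|
| Four contrasts, each at 0.05 | 15-17% |
| Contrasts read only after a significant omnibus F | 7-8% |
| H1 contrast only, either outcome suffices, outcomes independent | 1 − 0.95² = 9.75% |
| H1 contrast only, both outcomes required, outcomes independent | 0.05² = 0.25% |

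With correlated outcomes the either-outcome figure falls slightly. The both-outcomes figure rises to about 0.9% at a correlation of 0.5. It can never exceed 5%, even if one effect is real.

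**5. Cost of Holm on the two H1 outcomes.** With 432 / 3 = 144 per arm and d = 0.30, power of a single contrast is about 72% at 0.05 and about 62% at the first Holm step (0.025). If both effects are d = 0.30, Holm's power per outcome is about 67-68%.

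**The case against.** The best defence is that the RQ5 label follows its place in the Objectives. The imagery headings form a primary block (H5, RQ5) and a secondary block (H6, RQ6), and Table 2 copies that division. RQ3 stands under a separate sociodemographic heading that does not mention primary outcomes. The H and RQ prefixes also separate hypotheses from questions. This stands as far as it goes: the label is not a flat contradiction of its heading. But the same heading calls RQ5 exploratory, Table 2 does not carry that word over, and the same moderator question ranks differently in the two components.

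A second defence is that the sentence on separate analyses concerns outcomes, not alpha, and that no alpha is stated for RQ5. That is correct. Running RQ5 at 0.05 is an assumption, although no other level appears in the plan.

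Third, planned contrasts may be meant to follow a significant F, and H1 predicts an effect on both outcomes. The plan settles neither point. Both would lower the risk calculator figure, and neither affects the imagery figure.

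A reader might go further and pool all ten Primary tests, obtaining up to 1 − 0.95^10 = 40.1% and concluding that a false primary finding is to be expected. The documents do not support that. The two factors are randomised separately, each component has its own question and its own sample-size calculation, and nothing in the plan makes them one family. Even the pooled figure is below one half, and it requires every null to be true.

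**Conclusion.** The point holds for the imagery component. RQ5 should not share Primary status with H5 while it is described as exploratory, has no sample-size basis and ranks above its counterpart RQ3. The size is about 26% against 5%, or about 22% if the interaction statistics correlate at 0.5. This assumes all nulls true, 0.05 per test, one test per moderator and H5 independent of the interactions.

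For the risk calculator component the finding is narrower: 15-17% ungated or 7-8% gated, with no stated success rule for H1. RQ1 is a closer call than RQ5, because the sample-size section names it alongside H1. The documents do not establish that H1 needs a multiplicity correction. That depends on whether one outcome is enough to claim it.

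**What to change.** **RQ5.** In Table 2, change the priority from Primary to Secondary, as for RQ3, and describe it as exploratory. Table 2 has no exploratory level, so the description needs a few words in the row or the text. H5 then becomes the sole primary test of the imagery component. This is a wording change; H5 keeps alpha 0.05 and its 352 completers.

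**RQ1.** State that ladder against table is read, for a given outcome, only after the H1 ladder-versus-text contrast is significant for that outcome. This is also wording only.

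**H1.** State whether support requires both outcomes or either one, and whether the contrasts depend on the omnibus F. If both are required, no adjustment is needed. If either suffices, Holm across the two outcomes is one option. Its cost is not trivial: about 72% falls to about 62% at the first step, for a contrast already below 80%.

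No adjustment between the two randomised factors is proposed.

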Baseline Survey 2 (Appendices L and M)	Immediately following completion of the mental imagery activity. The specific item wording is tailored based on which mental imagery condition is assigned (i.e., mental imagery vs. sleep), but the constructs assessed are the same for both conditions.	Message acceptance, ^[41] perceived clarity and vividness of images; ^[5, 9] and the following items obtained, developed, or adapted from: ^[5, 6, 9, 34] action plan; coping plan; action self-efficacy; recovery self-efficacy; and maintenance self-efficacy.
--	--	--

Part 2: Text Messaging

Mid-Intervention Text Message Surveys (Appendices X and Y)	1, 2, 3, and 4 weeks after Part 1	Perceived clarity and vividness of images; ^[5, 9] and the following items obtained, developed, or adapted from: ^[5, 6, 9, 34] action plan; coping plan; action self-efficacy; recovery self-efficacy; and maintenance self-efficacy.
--	-----------------------------------	--

Part 3: 90-Day Follow-Up

Follow-Up (Appendix BB)	90 days after Part 1	Comprehension; ^[31] physical activity behavior, ^[26, 27] sleep behavior, ^[9] tobacco use, ^[27] and the same items as in Baseline Survey 2 assessing intentions, action self-efficacy, cognitive and affective perceived risk, response efficacy, anticipated regret, and affective attitudes.
-------------------------	----------------------	---

Note: Race and education will be assessed during eligibility for recruitment stratification purposes only. Baseline Survey 1 excludes characteristics that will be assessed in the Risk Assessment questionnaire.

Statistical Considerations

Preliminary Analyses

We will begin by using descriptive statistics to understand the frequency and distributional properties of all items. For variables with non-normal distributions, data transformations or non-parametric tests will be used for subsequent analyses.

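### The test for change in minutes per week is chosen after seeing the data, and after a switch to a rank test the plan defines no analysis for the sex covariate or the moderation questions

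*Combined protocol and SAP*

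**What the plan says.** Under Statistical Considerations, Main Analyses, the assumptions of every test are to be checked, with normality and equal variance as the examples. Then: "If there are violations, non-parametric tests will be used instead". No diagnostic, threshold, replacement test or effect measure is given.

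The Preliminary Analyses section has its own rule: "For variables with non-normal distributions, data transformations or non-parametric tests will be used for subsequent analyses".

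The Main Analyses paragraph that contains the switch also sets three requirements for the model:

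- A fixed covariate: "Sex will be a covariate because there are no valid prediction models for male breast cancer".
- Further covariates, chosen from whatever the preliminary checks turn up.
- Interactions for the moderation questions: "Tests of moderation will be conducted by creating interaction terms between the risk presentation condition or mental imagery condition variables".

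For change in minutes per week, Table 2 lists a t-test for H5 (primary), an ANOVA with five moderators for RQ5 (also labelled primary), and a three-arm ANOVA with a ladder-versus-text contrast for H3 (secondary). The Sample Size Calculations section sizes H5 as a two-sided comparison of two means with d = 0.30, 80% power and alpha 0.05, giving 352 participants at 90 days. Eligibility Criteria restrict entry to people below 150 minutes per week.

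**The concern.** Two rules with different remedies govern the same outcome, and neither says what sets it off or what exactly replaces the planned test. An analyst could reach a t-test, a t-test on transformed data or a rank test for H5, and each would be consistent with the plan. The choice is made once the outcome data are visible.

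The switch also sits beside requirements that the usual rank tests do not meet. Mann-Whitney and Kruskal-Wallis tests have no place for a covariate or an interaction term. They compare distributions by rank and not mean change in minutes, so a switched H5 result would no longer answer the question for which the sample size was computed.

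**Working it through.** **1. The plan's own figure.** Inputs from Sample Size Calculations: d = 0.30, two-sided alpha 0.05, power 80%, two equal groups. The normal approximation gives n per arm = 2(1.960 + 0.8416)²/0.30² = 174.4, so 175. The exact noncentral t gives 175.4, so 176 per arm, or 352 in total, with power 0.801. The stated 352 is reproduced. Enrolment is 352/0.70 = 502.9, so 503, against 500 stated (500 × 0.70 = 350). The number stands for a test of means.

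**2. How likely is a switch?** The documents give no SD, distribution or pilot data for minutes, so this step rests on assumptions. Shapiro-Wilk at 0.05 on 352 residuals was taken as the trigger.

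| Assumed change score | Rule fires |
|---|---|
| Exactly normal | 5% |
| Mild skew from a floor at zero minutes | 69–85% (95% if 15% of participants carry the gain) |
| Heavy-tailed, t with 5 df | 96% |
| Gamma or lognormal follow-up minutes with 20% zeros | 100% |

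**3. What is left after a switch.**

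| Analysis | Needs | With the test named in Table 2 | With Mann-Whitney or Kruskal-Wallis |
|---|---|---|---|
| H5 | Sex covariate, mean change | Mean change yes; a t-test has no covariate | Neither |
| RQ5 | Sex, interactions | Available in the linear model | Neither |
| H3 | Sex, ladder-versus-text contrast | Available in the linear model | Contrast as a pairwise rank test; no sex term |
| RQ3 (comprehension, intentions) | Sex, interactions | Available in the linear model | Neither, if these outcomes trigger the rule |

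**4. Power after a switch.** If the data were normal, the rank test's relative efficiency is 3/π = 0.955. Power at 352 is then 0.783, and 352/0.955 = 368.6, so 369 completers would restore 80%. At the lower bound for a pure location shift, 0.864, power is 0.741 and 352/0.864 = 407.4, so about 408 completers would be needed.

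With skewed data the answer depends on how the gain is spread. The simulations below use 176 per arm, zero-inflated skewed minutes and a mean gain of 0.30 SD of the control-arm change score. Shapiro-Wilk rejected in every trial.

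| Spread of the gain | t-test power | Mann-Whitney power |
|---|---|---|
| Uniform shift | 79% | 94% |
| Concentrated in 15% of participants | 70% | 54% |
| Proportional to follow-up minutes | 66% | 47% |

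A separate run with the following shapes agrees with all six figures to within two percentage points: baseline uniform on 0–150 with 25% set to zero; follow-up gamma (shape 1.2, scale 80) with 20% set to zero; both rounded to 10 minutes.

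The t-test falls below 80% in the last two rows because an uneven gain widens the treated arm. For the 15% case with those shapes, the control SD is 100.3, the mean gain is 0.30 × 100.3 = 30.1 minutes, and each responder gains 30.1/0.15 = 201 minutes. The added variance is 0.15 × 0.85 × 201² ≈ 5,150. The averaged variance is 100.3² + 5,150/2 ≈ 12,635, so the SD is 112.4 and d is 30.1/112.4 = 0.268. The noncentrality is 0.268 × √88 = 2.51, which gives power of about 71%, in line with the simulated 70%.

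**5. Is the switch needed to control error?** Across the five shapes in the trigger simulations (normal, heavy-tailed, mild skew, gamma, lognormal), the t-test's null rejection rate was 0.044–0.052. In the zero-inflated skewed setting, the t-test, Mann-Whitney, baseline-adjusted linear model with HC3 errors and two-stage rule were all near 5%. A significant normality test at this size therefore does not show that the test of means is unsafe.

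**The case against.** Several stronger readings are tempting, and the documents do not support them.

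- **The rule is certain to fire.** No distribution or trigger is given. The results above run from 5% to 100% according to shape, so *likely* is as far as one can go.
- **The plan prescribes Mann-Whitney or Kruskal-Wallis.** It names neither. Rank ANCOVA, aligned-rank methods, and permutation or bootstrap tests of means are also non-parametric, and some keep the covariate, the interaction or the mean. The gap is that no method is named.
- **The contrasts are lost.** Ladder versus text and ladder versus table can be run as pairwise rank tests.
- **The switch costs power or inflates error.** Under normality the loss is about two points; under a uniform shift on skewed data there is a gain. The two-stage rule held its level in the simulation.
- **The switch is what drops sex from H5.** The t-test in Table 2 has no covariate to begin with, so that conflict precedes any switch. The reason given for the sex covariate concerns the risk display, but the sentence stands in a paragraph covering all hypotheses and is not restricted.

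A fair reply on the remedy is that naming the diagnostic, the fallback and its covariate handling would also close the gap. That is true of the under-specification. It would still leave the test, and the quantity tested, to depend on the data.

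**Conclusion.** The concern holds as under-specification with a practical consequence. The H5 test depends on the data under two unreconciled rules. A switch is likely for change in minutes per week. After it, the sex covariate and the RQ5 interactions have no defined analysis, and the same applies to RQ3 if its outcomes trigger the rule. A rank test would not test the mean difference behind the 352.

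The size is a spread in Mann-Whitney power of about 47% to 94% for a mean gain of 0.30 SD, against about 66% to 79% for the t-test. These figures rest on assumed zero-inflated skewed shapes and an assumed Shapiro-Wilk trigger, so they illustrate how strongly power depends on the form of the effect and do not predict this trial. A reader should not infer that a mean-based analysis guarantees 80% power: when the gain is concentrated or proportional, the t-test also falls below it. No distributional evidence was available for comprehension or intentions, so the argument for those outcomes is consistency only.

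**What to change.** For H3, H5 and RQ5, replace both the switching rule and the transformation rule with one pre-specified linear model, used whatever the distribution. It contains the randomised factors, sex and baseline minutes, with HC3 or bootstrap standard errors. Run the contrast and the interactions inside that model. Name one rank-based analysis and report it as a sensitivity analysis only.

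Apply the same fixed-model rule, without baseline minutes, to comprehension and intentions (H1, RQ1, RQ3), so that the plan has a single rule. This also settles how sex enters H5.

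The cost is SAP wording and standard software. Physical activity is already collected in the eligibility screener, and the 352 stands for the test of means. The downside is that a rank test would have had more power if the effect is a uniform shift on skewed data (94% against 79% above); the sensitivity analysis would show such a result but would not carry the primary conclusion.
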